1.2 Objectives

The primary objective is to evaluate the effect of a transitional care intervention (“TARGET” intervention) prioritized to higher-risk medical patients on the composite of 30-day unplanned readmissions and death.

Secondary objectives are to evaluate:

- the effect of a targeted transitional care intervention to higher-risk medical patients on hospital utilization, medication adherence, patient’s perspective on quality of transition of care and time to readmission or death (whatever comes first),
- the effect of a targeted transitional care intervention on the primary outcome in subgroup population of patients with intermediate (simplified HOSPITAL score of 4 or 5) compared to high risk of readmission (simplified HOSPITAL score ≥ 6), who suffer from common chronic diseases (diabetes, chronic heart failure, COPD or cancer), and according to living place, living status and health insurance,
- the cost-effectiveness of the transitional care intervention.

2 Study methods

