2.2 Randomization

Allocation of patients is done when all inclusion and exclusion criteria are satisfied. Patients are randomly assigned in a ratio of 1:1 to one of two treatment arms:

- 1) Transitional care (intervention) or
- 2) Usual care (control).

Allocation of patients is done with the data management system (REDCapTM) that also hosts the electronic case report forms (eCRFs). Allocation is stratified by:

- Discharge site (Hôpital Fribourgeois, Centre hospitalier Bienne, CHUV Lausanne, Hôpital neuchâtelois)
- Readmission risk category according to the simplified HOSPITAL score (intermediate vs high risk, i.e. a HOSPITAL score of 4 or 5 vs ≥ 6)

The readmission risk category is documented on eCRF “Eligibility” by variable `strat_1`, the discharge site is coded via the patient ID. The random allocation is performed centrally within the data management system using permuted block with random block sizes of 2, 4 and 6. Investigators receive the allocation only after the eCRF “Eligibility” has been completed. The allocation is documented by variable `alloc_a_group` on eCRF “Eligibility”.

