2.3 Sample size

Because we will target patients at higher risk of readmission, we hypothesize that the intervention could reduce the relative risk of readmission by 25%, i.e. more than the 18% reduction found in a recent meta-analysis where patients were mostly not at high risk for readmission. Based on previous findings, the expected 30-day readmission and death rate for patients at intermediate or high risk according to the simplified HOSPITAL score is around 27%. Allowing for 10% loss to follow-up, we determine that we will need 1,380 patients for the study to have 80% power, i.e. 690 in each arm.

The intervention phase (randomized controlled trial) will be restricted to the eligible patients who are at intermediate to high risk of 30-day readmission according to the simplified HOSPITAL score, i.e. $\geq 4/13$ points. We estimate to have around 18,000 patients discharged during the 20-month study period, 30% of which (5,400) will be at higher-risk for a 30-day readmission or death. This should be enough to reach the targeted sample size within the study time frame.

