4.2 Confidence intervals and p-values

A level of statistical significance of 5% will be used. All statistical testing will be two-sided. All tests will be accompanied by an effect measure (transitional care vs usual care) with a 95% confidence interval (95% CI).

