4.4 Analysis populations

4.4.1 Full analysis set (FAS)

The full analysis set (FAS) will include all randomized subjects. Following the intent-to-treat (ITT) principle, subjects will be analyzed according to the treatment they are assigned to at randomization regardless of the treatment actually received.

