Each item of the CTM-3 score will be summarized by treatment group using relative and absolute frequencies. The number of patients with a yes on all items will be compared between treatment groups using a Mantel-Haenszel risk difference with a two-sided 95% CI⁴ and a Cochran-Mantel-Haenszel test, both stratified for the stratification factors used in randomization.

The costs of readmission will be analyzed by linear regression with the treatment group and the stratification factors used in randomization as covariates. The treatment effect will be presented as

CTU Bern	SAP for TARGET-READ phase 2	05.03.2019
	Version 1.0	Page 21 27

mean difference with 95% CI and a p-value. Model assumption will be checked visually using plots of residuals (residuals vs fitted values, QQ-plot). If model assumptions are violated, transformation of the outcome (e.g. log), more robust methods (e.g. robust standard errors or robust regression) or non-parametric methods (e.g. Wilcoxon-Mann-Whitney test or van Elteren's test) will be considered.

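### Readmission costs: the planned effect is a mean difference, but after a residual check that will very likely fail, most of the permitted alternatives no longer estimate it

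*SAP*

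**What the plan says.** Section 6.3.1.2 analyses readmission costs by linear regression on treatment group and the randomization strata. The effect is reported as a mean difference with a 95% CI and p-value. Residuals are then judged by eye, including on a QQ-plot. If the assumptions appear violated, the SAP will consider "transformation of the outcome (e.g. log), more robust methods (e.g. robust standard errors or robust regression) or non-parametric methods", the last illustrated by the Wilcoxon-Mann-Whitney and van Elteren tests. No order is given, no rule says which option applies, and nothing says that the mean difference remains the effect measure.

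Table 8 in section 6.2 defines the outcome only as costs_30d, continuous in CHF, with no derivation. It does not say whether a patient who was not readmitted is coded 0, or whether planned readmissions are costed.

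Two other places bear on this. Section 4.4.1 states: "The full analysis set (FAS) will include all randomized subjects". Section 1.2 lists as an objective "the cost-effectiveness of the transitional care intervention".

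**The concern.** Thirty-day readmission cost in an all-randomized population is typically a large spike at zero plus a skewed tail. Its residuals are not normal, and this can be foreseen from the design rates. The visual check is therefore less a safeguard than a likely route into the fallback list.

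The options on that list answer different questions:

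- **Log transformation** is undefined at zero. Dropping the zeros compares only readmitted patients, a subset formed after randomization. Adding a constant makes the result depend on that constant.
- **Robust regression** treats the readmitted minority as outliers and settles on the zeros.
- **Rank tests** mainly compare how many patients were readmitted, which the trial already analyses elsewhere.
- **Robust standard errors** leave the mean difference in place.

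The choice would be made after the data are seen. Section 2.8 lists the statistician among the unblinded staff, and section 7 confirms that blinded analysis was dropped. The options can differ in size and even in sign.

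**Working it through.** **1. The design figure reproduces.** The inputs from section 2.3 are a control rate ("the expected 30-day readmission and death rate for patients at intermediate or high risk according to the simplified HOSPITAL score is around 27", in per cent), an effect ("the intervention could reduce the relative risk of readmission by 25" per cent) and the target ("Allowing for 10% loss to follow-up, we determine that we will need 1,380 patients for the study to have 80% power, i.e. 690 in each"). Section 4.2 gives the test level ("A level of statistical significance of 5% will be used. All statistical testing will be two-sided") and section 2.2 the allocation ("Patients are randomly assigned in a ratio of 1:1"). The intervention rate is 0.27 × 0.75 = 0.2025. The usual two-proportion formula without continuity correction gives 621 per arm, and 621 / 0.90 = 690 per arm, 1,380 in total. These rates are therefore the plan's own working rates.

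**2. Share of patients without an event.** Control 1 − 0.27 = 73.0%. Intervention 1 − 0.2025 = 79.75%. Pooled 1 − (0.27 + 0.2025)/2 = 76.4%. If these patients are coded 0 CHF, the share of zero costs moves as follows (the ranges are assumptions):

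- deaths without readmission in 2% to 10% of patients raise it to 78% to 86%;
- drop-outs of 5% to 10% set to zero raise it to 78% to 79%;
- costed planned-only readmissions in 2%, 5% or 10% lower it to 74%, 71% or 66%.

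Zeros are the majority throughout.

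**3. What each option returns.** Simulation with 690 per arm, 300 replicates, strata omitted. Readmitted patients have lognormal costs (log-SD 1, assumed control mean 15,000 CHF) and all others cost 0. With 27% against 20.25% readmitted and equal cost per readmission, the true mean difference is 0.2025 × 15,000 − 0.27 × 15,000 = −1,012.5 CHF.

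| Method | Result |
|---|---|
| Linear regression, model-based or robust SE | −1,018 CHF; robust 95% interval covers in 96% |
| Huber regression | −0.8 CHF |
| Log(cost + 1) | −0.62, on a scale set by the added constant |
| Log of positive costs only | 0.00 |
| Mann-Whitney probability | 0.466 |

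Residuals were clearly non-normal (Shapiro-Wilk p < 10⁻⁶) in every replicate. With intervention cost per readmission at 20,000 CHF the true mean difference is 0.2025 × 20,000 − 0.27 × 15,000 = 0. Log(cost + 1) then gives −0.56 and log of positive costs +0.28, which are opposite signs from the same data.

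**4. Why rank tests track the readmission proportion.** Let p_t and p_c be the readmission proportions and θ the probability that a readmitted intervention patient costs more than a readmitted control patient. With tied zeros, the Mann-Whitney probability is

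0.5 + (p_t − p_c)/2 + p_t p_c (θ − 0.5).

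At the design rates the proportion term is (0.2025 − 0.27)/2 = −0.034. The cost term has weight 0.2025 × 0.27 = 0.055. Even with θ = 1 it adds only 0.027, so the probability stays below 0.5 however expensive the intervention arm's readmissions are.

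**5. Rejection rates under equal true mean cost.** Assumptions: control rate 27%, lognormal costs with CV 1, 690 per arm. Intervention cost per readmission is raised by a factor r and the readmission rate is 27%/r, so mean cost is equal.

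| Cost per readmission, intervention vs control | Readmission rate, intervention | Mean test rejects | Wilcoxon rejects |
|---|---|---|---|
| equal | 27.0% | about 4–6% | about 5% |
| +10% | 24.5% | about 4–6% | about 14% |
| +20% | 22.5% | about 4–6% | about 34% |
| +33% | 20.25% | about 4–6% | about 69% |

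**6. The reverse case.** Both arms have 27% readmitted, and cost per readmission is 25% lower with the intervention (11,250 against 15,000 CHF). The mean difference is 0.27 × (11,250 − 15,000) = −1,012.5 CHF. The variance per patient is p m²(1 + CV²) − (p m)², which is 105.1 million for control and 59.1 million for intervention. The standard error is √(164.2 million / 690) = 488 CHF. The ratio is 1,012.5 / 488 = 2.07, so the mean test has power of about 55%. Wilcoxon rejects in about 10%.

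**The case against.** The primary specification is already right: linear regression, mean difference, strata as covariates. Robust standard errors are on the list, and the alternatives are only to be considered. With 690 per arm a statistician could reasonably keep the linear model despite a poor QQ-plot. This stands. A reader might infer that a switch away from the mean is certain; the SAP permits it but does not require it.

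The zero share is also an inference. The SAP states neither the coding nor the scope of costs_30d, so three quarters cannot be read as a guaranteed minimum. If the field is blank for patients who were not readmitted, there is no spike at zero. The regression would then compare only readmitted patients and lose the protection of randomization, which is no better.

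A reader might take the 69% as the expected error rate. It is the end of an assumed range in which costlier readmissions exactly offset the planned 25% reduction (1/0.75 = 1.33). With no difference in either component, Wilcoxon holds its level. With equal cost per readmission, Huber, log(cost + 1) and the rank measure all share the sign of the mean difference.

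Nor is the rank test invalid. In these examples the cost distributions do differ, and rejecting is correct for the rank hypothesis. The error arises only if the result is read as a saving in CHF. Section 6.3.3 itself pairs Wilcoxon with the Mann-Whitney statistic in the crude analyses.

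Finally, the SAP sets out no cost-effectiveness calculation, so it cannot be said that one would use this regression's fallback. What remains is that mean cost is the planned effect here and that the list allows it to be abandoned without a rule.

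**Conclusion.** The point holds as a weakness in pre-specification. The SAP names a mean difference and then, on a visual check that will very likely fail, allows an unordered choice in which only robust standard errors still estimate it. Depending on how readmission frequency and cost per readmission move, a rank test can reject in about 5% to 69% of trials with equal mean cost. It can also find a difference in about 10% of trials where the mean test finds it in about 55%. Huber regression returns close to 0 CHF when the true difference is about −1,012 CHF.

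These sizes rest on assumed lognormal costs, an assumed 15,000 CHF per control readmission, zero coding for patients who were not readmitted, and omitted strata. The CHF level does not affect the mean-test or Wilcoxon rejection rates. That zeros form the majority follows from the plan's own rates once zero coding is assumed, and holds at about 66% to 74% if planned readmissions are costed on the assumed shares. The primary outcome and the sample size are unaffected.

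**What to change.** In section 6.3.1.2, keep linear regression on group and strata, with the adjusted mean difference in CHF, whatever the residual plots show. Base its confidence interval and p-value on robust (sandwich) standard errors or on a bootstrap stratified by arm and randomization stratum, and name which one now. Move log, robust-regression and rank analyses to supplementary status, each reported with its own effect measure and not as a cost saving in CHF.

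In Table 8, state that patients who were not readmitted enter with cost 0, and say whether costs_30d includes planned readmissions.

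The cost is a few lines of SAP text. Intervals may be somewhat wider than under a transformation. No data collection, sample size or primary analysis changes.

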6.3.2 Secondary analyses

All outcomes will also be analyzed in the PPS. Only patients without missing value for the respective outcome will be considered (complete cases).

6.3.3 Sensitivity analyses

The following sensitivity analysis will be included for all outcomes:

- 1) Without early readmissions. The primary endpoint will be re-analyzed excluding the patients with unplanned readmissions up to the day after index discharge (i.e. unplanned_1_in - disch_date_index <=1)
- 2) No stratification: All outcomes will be analyzed in crude analyses not adjusting for stratification factors. Binary outcomes will be compared by chis-squared test, continuous outcomes by Student's t-test or the Wilcoxon-Mann-Whitney test, count outcomes using an exact Poisson-test and time-to-event outcomes by a log-rank test. Effects will be presented as non-stratified risk difference, mean difference or Mann-Whitney statistic (i.e. the probability that a random patient from the intervention group will have a higher value than a random patient from the control group), incidence rate ratio, and restricted mean survival time difference, respectively, with 95% CI.
- 3) Primary endpoint based on survival methods. The risk of readmission or death at 30 days for both groups and the risk difference between groups will be calculated with 95% CI and p-values from a z-test using a) a flexible parametric survival model for time to unplanned readmission or death with the group and stratification factors as covariates and b) from the Kaplan-Meier-estimator for time to unplanned readmission or death not using the stratification. CIs for the risk differences and the z-test will be calculated using delta method standard errors and a normal approximation.
- 4) Non-parametric unplanned readmissions: The risk of unplanned readmission at 30 days in the presence of the competing risk of death will be calculated for each group using the non-parametric cumulative incidence function estimator with 95% CI according to Choudhury et al⁸. Stratification will be ignored.

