6.1.2 Secondary outcomes

- Number of deaths within 30 days after discharge
- Number of patients with unplanned readmission within 30 days after discharge
- Time to first unplanned readmission or death within 30 days
- Main cause of readmission or death
- Post-discharge health care utilization within 30 days after discharge from index hospitalization:
 - number of unplanned hospital readmissions
 - number of planned hospital readmissions
 - total number of unplanned days of hospitalizations
 - total number of planned days of hospitalizations
 - number of emergency room visits
 - number primary care provider visits
- Patient's perspective (satisfaction) on quality of transition of care between hospital and home assessed by the three-item care transition measure (CTM-3) at 30 days
- Costs of readmission at 30 days

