6.2 Outcome derivation

Table 8: Derivation of primary and secondary outcomes.

Outcome	eCRF sheet	Variable	Variable type	Derivation	Outcome type
Primary: Unplanned readmission or death within 30 days after discharge	Baseline Characteristics	discharged_alive	Binary: No, Yes	discharged_alive==No or	Binary
	Follow-up calls	reas_pat_notre_d3, reas_pat_notre_d14	Categorical: Death, No answer, Other	reas_pat_notre_d3==Death or	
	Outcomes 30 days	death_d30	Binary: No, Yes	reas_pat_notre_d14==Death or	
Deaths within 30 days after discharge	Baseline Characteristics	unplanned	Integer: 0-6	death_d30==Yes or	Binary
		discharged_alive	Binary: No, Yes	unplanned>=1	
		reas_pat_notre_d3, reas_pat_notre_d14	Categorical: Death, No answer, Other	discharged_alive==No or	
Outcomes 30 days	Follow-up calls	death_d30	Binary: No, Yes	reas_pat_notre_d3==Death or	Binary
		reas_pat_notre_d14	Categorical: Death, No answer, Other	reas_pat_notre_d14==Death or	

Outcome	eCRF sheet	Variable	Variable type	Derivation	Outcome type
Unplanned readmission within 30 days after discharge	Outcomes 30 days	unplanned	Integer: 0-6	unplanned>=1	Binary
Time to first unplanned readmission or death	Baseline Characteristics	disch_date_index, baseline_death	Date: dmy	Time: min(30, min[baseline_death, date_death_d3, date_death_d14, date_death_d30 unplanned_in_1, lcontact_date] – disch_date_index)	Time-to-event
	Follow-up calls	date_death_d3, date_death_d14	Date: dmy		
	Outcomes 30 days	date_death_d30, unplanned_in_1	Date: dmy		
	End of Study	lcontact_date	Date: dmy	Failure: Primary==Yes	
Main cause of readmission or death	Follow-up calls	cause_death_d3, cause_death_d14	Free text	Tabulated free text fields will be manually categorized	Categorical
	Outcomes 30 days	dx_read30, cause_death_d30	Free text		
Number of unplanned hospital readmissions	Outcomes 30 days	unplanned	Integer: 0-6	-	Count
Number of planned hospital readmissions	Outcomes 30 days	planned_readmission	Integer: 0-8	-	Count
Total number of unplanned days of hospitalizations	Outcomes 30 days	unplanned_x_in, unplanned_x_out	Date: dmy	unplanned_x_out – unplanned_x_in	Count
Total number of planned days of hospitalizations	Outcomes 30 days	tot_rehosp_days_planned	Continuous: days	-	Count
Number of emergency room visits	Outcomes 30 days	nb_edvisits	Integer	-	Count
Number primary care provider visits	Outcomes 30 days	nb_pcpvisits	Integer	-	Count

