6.3.1.2 Analysis of secondary outcomes

The number of patients that die will be compared between treatment groups using a Mantel-Haenszel risk difference with a two-sided 95% CI⁴ and a Cochran-Mantel-Haenszel test, both stratified for the stratification factors used in randomization.

The risk of 30 day unplanned readmissions in each group will be estimated using the cumulative incidence function with death as competing event calculated from flexible parametric survival models (e.g. using `stpm2` followed by `stpm2_standsurv` in Stata)^{5,6}. Groups will be compared using the cumulative incidence difference with 95% CI and a z-test, based on delta method standard errors and a normal approximation. We will also report the cumulative incidence of the competing event (death without readmission) for each group and the risk difference between groups.

Time to unplanned readmission or death will be graphically depicted by Kaplan-Meier curves for each treatment group. Groups will be compared using a log-rank test stratified for the stratification factors used in randomization. As an effect measure, we will use the restricted mean survival time truncated at 30 days calculated using flexible parametric survival models with the group and factors used at randomization as covariates⁷. The restricted mean survival time for each group and the difference between groups will be reported with 95% CI and a p-value.

The main cause of readmission or death will mainly be analyzed with descriptive statistics. The number and proportion of patients in each category will be shown for both groups.

Count outcomes (number of hospital readmissions, number of days of hospitalization, number of emergency room visits, number of primary care provider visits) will be presented with number of patients, person-time and incidence rate with 95% CI. Groups will be compared using a negative binomial regression with the group and the stratification factors as covariates and the observation time as offset. An incidence rate ratio with 95% CI and p-value will be reported. In case of an excess of zeros and overdispersion that cannot be modeled by the negative binomial distribution we will consider zero-inflated negative binomial regression (e.g. using function `zeroinfl` from R package `pscl`).

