6.3.4 Subgroup analyses

The primary outcome will be analyzed for subgroups defined by the stratification factors for randomization:

- Risk for readmission (HOSPITAL score of 4 or 5 vs ≥6)
- Clinical site
- Diabetes
- Chronic heart failure
- COPD
- Cancer

CTU Bern	SAP for TARGET-READ phase 2	05.03.2019
	Version 1.0	Page 22 27

- Living place (nursing home vs rest)
- Living status (alone vs rest)
- Health insurance (Semi-private and private vs rest)

Table 9: Derivation of subgroups

Subgroup	eCRF sheet	Variable	Categorization
HOSPITAL score	Eligibility	hosp_score_simple	if hospital_change==no: hosp_score_simple > 5
	Baseline Characteristics	hosp_change	else:
		hosp_score_simple_2	hosp_score_simple_2 > 5
Clinical site	-	record_id	substr(record_id,1,3)
Diabetes	Index Diagnosis	comorbidities__5	comorbidities__5==checked
Chronic heart failure	Index Diagnosis	main_dx_at	main_dx_at==Heart failure or
		comorbidities__9	comorbidities__9==checked
COPD	Index Diagnosis	main_dx_at	main_dx_at==COPD exacerbation or
		comorbidities__7	comorbidities__7==checked
Cancer	Index Diagnosis	main_dx_at	main_dx_at==Neoplasm or
		comorbidities__8	comorbidities__8==checked
Living place	living_type	Categorical: Home, Protected apartment, Nursing home, Other, Unknown	living_type==Nursing home
Living status	living_st	Categorical: With spouse/partner, With another person, Alone, Unknown	living_st==Alone
Health insurance	insur	Categorical: Base, Base+compl, Semi-private, Private, Other, No insurance	insur==Semi-private or insur==Private

Subgroups will be analyzed using regression models with the treatment group, the subgroup and their interaction and the stratification factors used at randomization as covariates. If possible, a binomial model with identity link function will be used and the effects will be reported as risk differences with 95% CIs. Otherwise, a Poisson model with identity link and robust standard errors (leading to risk differences) or a binomial model with logit link (leading to odds ratios) will be considered. Models with and without interaction will be compared using a likelihood ratio test and the p-value will be reported as p-value for interaction. Results will be presented in a forest plot.

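### The crude sensitivity analysis tests hospital days with an exact Poisson test, whose true error would be about 18–58% instead of 5% for assumed mean stays of 3–12 days

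*SAP*

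**What the plan says.** Section 6.3.3, item 2, repeats the analysis of all outcomes without the stratification factors and compares "count outcomes using an exact Poisson-test", with an incidence rate ratio and 95% CI as the effect measure. It names no method for that interval and makes no exception for any count.

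Hospital days are among the counts. The list in section 6.3.1.2 begins "Count outcomes (number of hospital readmissions, number of days of hospitalization, number of emergency room visits". Table 8 (section 6.2) gives the outcome type Count to unplanned days, derived as "unplanned_x_out – unplanned_x_in", and to "Total number of planned days of hospitalizations".

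For the same outcomes the main analysis is more careful. In section 6.3.1.2, "Groups will be compared using a negative binomial regression", with observation time as offset, and a zero-inflated model is held in reserve: "In case of an excess of zeros and overdispersion that cannot be modeled by the negative binomial distribution".

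**The concern.** The exact Poisson test is valid when events occur independently, so that the variance of the count equals its mean. A hospital day is not such an event. One readmission produces a run of consecutive days, and most patients contribute none, so the variance per patient is several times the mean. The test then takes a handful of long stays as strong evidence. Section 6.3.1.2 recognises the problem and item 2 drops the protection without giving a reason.

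The crude result will be read beside the main one. A chance imbalance in a few long stays could appear significant in the crude analysis while the main analysis shows nothing. Item 2 is also meant to show what happens when stratification is ignored. As written it changes the variance model at the same time, so a disagreement could not be put down to stratification.

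**Working it through.** **Inputs from the SAP.** Two-sided 5% level (4.2); 1:1 allocation (2.2); 690 per arm (2.3); 30-day window (6.1.2: "Post-discharge health care utilization within 30 days after discharge from index hospitalization").

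**The plan's own figure.** With 27% and 27% × 0.75 = 20.25%, pooled mean 23.625%:

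n = [1.96·√(2 × 0.23625 × 0.76375) + 0.8416·√(0.27 × 0.73 + 0.2025 × 0.7975)]² / 0.0675² ≈ 620.5, so 621 per arm.

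Then 2 × 621 / 0.90 = 1,380, as stated. The 690 per arm can be relied on.

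**Assumptions not in the SAP.** No treatment effect; equal person-time; at most one stay per patient, starting at a uniform time; days cut at day 30. Unplanned stays: 15–25% of patients, mean 3–12 days. Planned stays: 5–10% of patients, mean 3–8 days.

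**Formula.** Let a share p of patients have one stay with mean m and variance s². Before any cut at day 30, the variance-to-mean ratio of days per patient is

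φ = m(1 − p) + s²/m,

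and the actual two-sided error of a nominal 5% Poisson test is approximately 2[1 − Φ(1.96/√φ)]. The number of patients does not enter.

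- Fixed 3-day stays, p = 0.25: φ = 3 × 0.75 = 2.25; 1.96/1.5 = 1.307; error about 19%.
- Fixed 5-day stays, p = 0.25: φ = 3.75; 1.96/1.936 = 1.012; error about 31%.
- Geometric stays, mean 5 (s² = 20), p = 0.15: φ = 4.25 + 4 = 8.25; 1.96/2.872 = 0.682; error about 50%.

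Fixed-length stays are the mildest case for a given mean, because s² = 0.

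**Simulation, unplanned days cut at day 30.** Exact conditional binomial test on total days; 48 scenarios of 3,000 trials (15, 20 or 25% readmitted; exponential, log-normal, gamma or fixed stays):

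| Mean stay | φ | Type I error | Robust / Poisson SE | Coverage of Poisson Wald 95% CI |
|---|---|---|---|---|
| 3 days | 2.2–4.7 | 18–36% | 1.5–2.2 | 63–81% |
| 5 days | 3.7–7.3 | 30–47% | 1.9–2.7 | 53–70% |
| 8 days | 5.8–9.9 | 41–52% | 2.4–3.1 | 47–59% |
| 12 days | 8.6–12.1 | 48–58% | 2.9–3.5 | 42–51% |

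A second set of simulations, with other stay-length distributions and 2,000 trials per scenario, gave 18–35% for 3-day stays and 30–59% for 5–12-day stays cut at day 30. Without the cut, 5–12-day stays gave 32–68%. Truly Poisson data gave 4.8%, so the inflation is not produced by the code.

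**Planned days.** 21–53%.

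**Readmission and visit counts.** 5–11% at φ of 1.0–1.5, and 15–26% at φ of 2.0–3.0.

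**What the interval would look like.** Take 20% readmitted, geometric stays of mean 5 days (4.3 after the cut, φ = 6.61) and an observed ratio of 1.0. Days per arm: 0.20 × 690 × 4.3 ≈ 593. Poisson SE of the log ratio: √(2/593) = 0.058, giving 0.89–1.12. Multiplying the SE by √6.61 = 2.57 gives 0.149 and an interval of about 0.75–1.34.

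**Alternatives under the same null.** Robust Poisson: 3.9–6.1% in all scenarios. Permutation test (400 trials, exponential stays, 20% readmitted): 4.8% at mean 5 days and 6.3% at mean 8. Negative binomial with group only: 0.4–3%, thus conservative, but from short runs of 250 trials.

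**The case against.** The reach is small. Item 2 is a crude sensitivity analysis of secondary outcomes, no decision in the SAP depends on it, and the main rate ratio will stand next to it. Planned days were added only because they are of interest (section 7). This is right, and it limits the weight of the point without making the test valid.

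The percentages rest on stay lengths and readmission shares that the SAP does not give, and nothing in it favours 5–12 days over 3. That also stands, so the full range of 18–58% is the fair statement. Even its lowest value is more than three times the nominal level. The coverage figures are illustrative, since item 2 names no interval method.

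The smaller inflation for readmission and visit counts holds only if their dispersion is low. At a variance-to-mean ratio of 2–3 they overlap with the 3-day result for hospital days.

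Section 6.3.4 does mention "a Poisson model with identity link and robust standard errors", but only as a fallback for a binary outcome. It shows that the method is familiar to the authors and is no precedent for rates of hospital days.

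Finally, robust Poisson also differs from the main model in how it handles variance. If the sole aim is to isolate stratification, the negative binomial model with group only is closer. It is an equally valid choice.

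**Conclusion.** The point holds. Item 2 as written applies a test that is invalid for two of the six count outcomes, unplanned and planned hospital days, and the SAP's own main analysis shows why. Under the assumptions listed above, the error for unplanned days is 18–36% at a mean stay of 3 days and 30–58% at 5–12 days; for planned days it is 21–53%. Poisson-based intervals for unplanned days would be about 1.5 to 3.5 times too narrow. The exact figures depend on the assumed stays. The direction does not, because any stay of several days pushes the variance above the mean. It should be corrected, but the trial's main conclusions do not depend on it.

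**What to change.** In section 6.3.3, item 2, replace the exact Poisson test for count outcomes by Poisson regression with treatment group as the only covariate, the same observation-time offset and robust (sandwich) standard errors, and report the rate ratio with 95% CI. The negative binomial model of section 6.3.1.2 with group only, or a permutation test of the rate ratio, would also do. One of them should be named in advance.

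Two small clarifications can go in with it; neither adds to the weight of the point:

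- Table 8: write unplanned days as the sum over stays, each capped at the end of the observation time used for the offset, and state that the recorded total of planned days covers the same window. The offset is capped at 30 days and the day count is not, so the two would differ if discharge dates after day 30 are recorded.
- Section 6.4: it refers to a Poisson regression for counts, where section 6.3.1.2 specifies negative binomial. Align the wording with 6.3.1.2.

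The cost is one sentence and two wording changes. The crude intervals for hospital days become wider. No new data are needed.
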